12.3 Protein Assays of Allograft Injury

We will evaluate both serum (systemic) and urine (local) protein expression specifically looking at factors associated with acute and chronic injury of the kidneys in patients undergoing kidney allograft transplantation by correlating these putative biomarkers with renal function and biopsy material as described in the statistical plan. The proteins listed include those associated with progressive deterioration of renal function in other settings, specifically kidney allograft dysfunction. Positive control proteins or peptides will be included as appropriate. Urinary results will be normalized to creatinine content. Markers for evaluation, their expected disease association, and method of measurement are shown in Table 8, as the study progresses this panel of markers or the core lab performing the assays may change.

Table 8. Proteins for Analysis of Renal Injury in Kidney Transplantation					
Tissue	Protein	AKI	CKI	CNI Toxicity	Methodology
Urine	NGAL	X	Unknown	Unknown	ELISA
"AKI"	NAG	X	Unknown	Unknown	Colorimetric assay
	IL-18	X	Unknown	Unknown	ELISA
	KIM-1	X	Unknown	Unknown	ELISA
	IP-10	AR	Unknown	Unknown	Luminex
	MIG	AR	Unknown	Unknown	Luminex
Urine	CTGF	No association	X/EMT	Unknown	ELISA
"IF/TA"	MMP9	No association	x	Unknown	ELISA
	Col Ia1	Unknown	X	Unknown	Western
	ColIIIa1	Unknown	X	Unknown	Western
	ColIVa3	Unknown	X	Unknown	Western
	Fibronectin	Unknown	X	Unknown	Western
	ICAM-1	Unknown	X	Unknown	ELISA
	VCAM-1	Unknown	X	Unknown	ELISA
	Laminin β2	Unknown	Unknown	CNI TOX	ELISA
	TGFβ	No association	X/EMT	CNI TOX	ELISA
	βIG-H3	Unknown	Unknown	CNI TOX	Western
	Osteoprotogerin	Unknown	X	Unknown	Luminex
	MIP-1d	Unknown	X	Unknown	Luninex
Urine	S100A4	Unknown	EMT	In vitro	ELISA
"EMT"	Vimentin	Unknown	EMT	In vitro	ELISA
	BMP-7	Unknown	EMT	Unknown	ELISA
Urine	Nestin	Unknown	Unknown	CNI TOX	Western
"Tox"	Caspase 1	Unknown	Unknown	CNI TOX	Colorimetric assay
	Caspase 3	Unknown	Unknown	CNI TOX	ELISA
Serum	Cystatin C	Х	Probable	Unknown	ELISA
	NGAL	X	Unknown	Unknown	ELISA
	CTGF	No association	x	Unknown	ELISA

Studies to quantify the expression of various cytokines, chemokines and growth factors at the protein level will also be undertaken using a standardized, cross-validated approach that will arise from the collaborative studies between participating CTOT and CTOT-C consortia described in the preceding paragraph. Sequential serum samples additionally may be analyzed for chemokines and cytokines and quantified using the Luminex[™] platform. Further target analysis exact assay SOP will be developed by the CTOT mechanistic assays consortia headed by Dr. [name] of Brigham and Women's Hospital for this particular assay.

12.4 Antibody Assays

12.4.1 Anti-HLA Antibody (Alloantibodies) and Non-HLA Antibodies

The presence of antibodies reactive to HLA molecules expressed on the renal allograft as well as non-HLA molecules such as MICA have been associated with both acute and chronic injury to the transplanted kidney. We will determine the presence, and if present the amount, of antibodies specific for HLA-A, B, C, DR, DQ α , DQ β , and DP β . We will use the LuminexTM solid phase testing platform. Serum samples will be collected for analysis at the time of transplantation, days 28 & 84, and weeks 28, 36, and 52. Donor specificity will be assigned based on the HLA type of the donor at the loci listed above.

The frequency and amount of antibodies to MICA will be determined using the approach developed by the CTOT/CTOT-C mechanistic assay consortium for detection of antibodies led by [name] at UCLA. The *de novo* development of donor-specific antibodies (DSA) will be compared to functional changes (assessed by eGFR) and histologic changes (as demonstrated by biopsy) for the 2 treatment groups.

12.5 Markers of Autoimmunity

The CTOT-15 study will explore the impact of the autoimmune response on graft function following pancreas transplantation. The hypothesis that is being tested is that markers of recurrent autoimmune disease will correlate with graft loss as defined by a return to insulin dependence. The details of the assay will be worked out at the time of the samples are available based on the needs of the study and technology. The assays for the cellular response against autoantigens are being developed in collaboration with the laboratory of [name] (Benaroya Insititute, Seattle). This work will compliment the current work conducted in the Clinical Islet Transplantation (CIT) consortium.

Whole blood will be collected, and peripheral blood mononuclear cells (PBMCs) and serum will be isolated from CTOT-15 participants at baseline, days 28 and 84, weeks 28, 36, and 52. In addition, these samples will be collected at the time of suspected rejection, prior to initiating therapy. The samples will be stored at the University of California, San Francisco for future analysis of markers of autoimmunity.

12.6 Genomics

We will isolate and save a DNA sample from each consented patient potentially to use in genomic analysis of polymorphisms for cytokine genes. There are several such gene polymorphisms that have been associated with increased risk of poor outcome post-transplant. While our goal is not to test the association between various genetic polymorphisms and graft outcome, it is possible that once our study is complete there may be questions regarding whether our results are independent of such polymorphisms and that it would be prudent to maintain small samples for analysis should such questions arise.

As already noted, prior studies using belatacept have been associated with acute rejection rates higher than standard therapy and the current study intends to optimize its use to minimize rejection or other toxicities. Analysis of gene polymorphisms in recipients may provide insight into allograft outcomes. Recently, polymorphisms in the CTLA4 gene have been described and associated with transplant outcome²⁵. We will analyze these polymorphisms as well as other others related to transplant outcomes²⁶. DNA will be isolated from the donor and recipient prior to treatment and subsequently analyzed. These results will be analyzed in terms of the primary and secondary endpoints of the study.

12.7 Pathology

12.7.1 Histology- Renal

Histologic examination will be performed at UCSF Pathology Laboratory. The centers will send 5 original stained slides (1 Trichrome or unstained, 1 PAS and 3 H&E) that were collected at times of for-cause biopsy (i.e., increase in serum creatinine, proteinuria, or other clinical symptoms) at the discretion of the site Investigator.

Fibrosis will be assessed using Trichrome and type III collagen stains in the Aperio digital images. Biopsy results will be reported using the Banff 2007 classification of renal allograft pathology. Furthermore, morphometric techniques performed on whole slide digital images in the central core laboratory will serve as adjunctive data to the routine histologic evaluation. Multivariate analysis will seek correlations with changes in any of the morphological parameters including cellular infiltration, vasculopathy, and fibrosis. C4d stains will also be performed on all biopsies if not performed and/or provided by the participating institution.

Morphological evaluations will be recorded in a standardized format, according to Banff '07 criteria. Primary data will be sent to the Statistical and Clinical Coordinating Center for final analysis. High-resolution images of entire sections of all stains from each biopsy will be acquired and archived in an Aperio Digital database system. Slide images will be stored at the UCSF (PI: [name]) for additional analysis, if needed.

12.7.2 Immunohistochemistry- Renal

The centers will send the remaining portion of the formalin fixed, paraffin embedded (FFPE) block at times of graft dysfunction/ for cause biopsies.

Immunohistochemical studies will assess collagen III deposition, subsets of inflammatory cell infiltrates, and other molecular markers to be determined in conjunction with genomic, proteomic, chemokine, and cytokine data. Since it is anticipated that the core for immunohistochemistry will be small, immunohistochemical stains will be tailored to biomarkers that show promise in the genomic, proteomic, chemokine, and cytokine studies. Remaining tissue will be stored at the UCSF (PI: [name]) until the end of the study (no more than 4 years) for additional analysis, if needed.

12.7.3 Histology- Pancreas

Histologic examination will be performed at UCSF. The centers will send stained slides (1- Trichrome or unstained slide and 3- H&E) at the times of standard of care and for cause biopsies, if available. Biopsy results will be reported using the Banff 2011 classification of pancreas allograft

pathology. Slide images will be stored at the UCSF (PI: [name]) for additional analysis, if needed.

12.8 Viral Testing

Viral infection following renal transplantation remains a significant source or recipient morbidity and mortality as well as a significant cause of allograft dysfunction and loss. We will test and quantify the presence of viremia. These tests will be completed in batch assay runs by a core laboratory, and results will not be available to the clinical centers. Detection of the following viruses will be performed by single assay Quantitative PCR: CMV, BKV, JCV, HHV6 and HHV7. EBV will be performed on serum. In collaboration with the Emory Clinical Laboratories we are developing quantitative viral load assays for HHV3 (varicella zoster), HHV6 (roseola), HHV7 (a potential co-factor for CMV disease), polyoma JC and the recently described polyoma WC and KI viruses. If cost-effective multiplexed or low-density arrays are developed, we will consider extending our studies to map the patterns of reactivation and viremia with these latent/chronic viruses.

12.9 Specimen Repository for Future Studies

An attempt will be made to collect amounts of volumes slightly in excess of the minimal required amount for the studies currently planned in order to allow specimens to be banked for use in new assays that have yet to be optimized of conceived or assays performed by other CTOT members not proposed as part of CTOT-15 such as analysis of miRNA, proteomic analyses, or ELISPOT. Appropriate informed consent will be obtained for both the collection and banking of samples and specimens.

Page 82 of 104

13 STATISTICAL CONSIDERATIONS AND ANALYTICAL PLAN

13.1 Statistical Analyses

CTOT-15 is a randomized open-label phase II clinical trial in which subjects who have received a SPK transplant are randomized 1:1 to treatment arms receiving (a) Thymoblobulin + methylprednisone induction followed by maintenance with tacrolimus + MMF, or (b) Thymoglobulin + methylprednisone induction followed by initial maintenance belatacept + MMF + gradually declining Tacrolimus so that ultimately they will be maintained entirely on a regime of belatacept and MMF. Analysis of the primary endpoint will be based on outcomes measured at 52 weeks post-randomization, while analyses of most secondary outcomes will be done on measurements taken at day 28, (baseline), day 84, and weeks 28, 36, and 52 post-randomization. The primary study objective is to evaluate the belatacept-based maintenance vs. tacrolimus- only maintenance, as a means of improving long term graft function without increasing the risks associated with the later of standard tacrolimus maintenance regimen. In addition, this study has a large number of secondary clinical and mechanistic objectives.

13.2 Endpoint Assessments

13.2.1 Primary Clinical Endpoint

The primary endpoint will be the week-52 eGFR. Mean eGFR of the belatacept group will be compared to the mean eGFR of the tacrolimus reference group within a mixed models repeated measures (MMRM) framework , wherein repeated measures of eGFR at weeks 4, 12, 28, 36 and 52 will be modeled as a linear function of time (and perhaps other baseline covariates) in the 2 treatment groups. At week-52, a contrast will be made between the eGFR mean of the belatacept group and the eGFR mean of the tacrolimus group. ANCOVA assumptions will be evaluated graphically via standard residual analyses. If the assumptions fail, a suitable transformation (e.g., natural logarithms) will be found and the data will be reanalyzed on the transformed scale. Results will be reported with p-values associated with the F-test for each contrast and the corresponding mean treatment differences with two-sided 95% confidence intervals. All tests of significance will be two-tailed at the 0.05 level.

Estimating the contrasts within the repeated measures framework will provide treatment comparisons that are robust to subject dropout bias as long as the dropout pattern is missing at random²⁷. Data are missing at random whenever the "missingness" mechanism is a function of observable relationships among the nonmissing responses and covariates. Using the methods of Ma et al.²⁸, we will evaluate the MAR assumption in the data prior to implementing the MMRM analysis. If the MAR assumption fails, we will consider more robust alternatives (e.g., pattern mixture modeling)²⁹.

A number of studies have shown RMANCOVA to be superior to analyses of completers or of data with LOCF imputations³⁰. Nonetheless, we will conduct 2 related sensitivity analyses: (1) replace the missing week-52 values with the corresponding nonmissing week 36 values of each subject, dropping anyone who is missing both week-36 and week-52 and perform the ANCOVA as currently specified; (2) include only the completers in the ANCOVA analysis (i.e., exclude all dropouts). The sensitivity analyses will be included as additional secondary analyses.

13.2.2 Secondary Clinical Endpoints

The secondary endpoints are defined in Protocol section 1.5.

The protocol defines 28 secondary clinical endpoints. The endpoints are to be computed and summarized by treatment and, in a few cases, by day/week and treatment. With the exception of specific AEs and lab parameters, proportions or means will be estimated for each treatment arm and tested for treatment differences through the use of a statistical model. The particular model to be used depends on the scale of measurement of the endpoint. The accompanying table lists each endpoint and its measurement scale (continuous, dichotomous, and ordinal). All tests of significance in all analyses will be made at the 0.05 level.

Dichotomous measures of prevalence and incidence will be analyzed with log-binomial regression models, wherein treatment effects will be estimated as relative risk ratios; the reference group will be the tacrolimus-thymoglobulin subjects. The log-binomial model (rather than logistic regression) is applied for prevalence and incidence analyses because model-based estimates of relative risk (RR) are both more desirable and appropriate for non-Poisson events that are expected to occur more commonly than in 10% of the cases. In such cases, logistic regression-based odds ratio (OR) estimates are poor estimators of the relative risk³¹,³²,³³,³⁴. It may be appropriate to treat some of the dichotomous outcomes as censored data; if this is the case, we will obtain RR estimates by fitting Cox regression models to the data³⁵.

The single ordinal secondary outcome variable (Banff cell-mediated AR score) will be analyzed in a proportional odds model³⁶ which may include additional covariates and interaction terms, as appropriate.

For continuous outcomes, we will test for differences in response means among the treatment arms by fitting normal theory analysis of variance (ANOVA) or analysis of covariance (ANCOVA) models to the original scores or to some normalizing-variance stabilizing transformation of them. For some endpoints, these models may be fit separately by month post-randomization (i.e., time will be treated as a by-variable and no repeated measures analysis will be performed). Repeated measures models will be fit to HbA1c data and to the slopes of eGFR vs. time regressions. The latter will be estimated in a mixed effects repeated measures model in which both treatment-group means (with 95% confidence limits) of the individual subject slopes and the individual subject slopes themselves will be estimated and tested for equality. Distributions of the individual slopes will be examined graphically and compared among the treatment groups.

Response type	Response	Measurement Scale	Summary Statistics	Models to test for treatment effects
Primary Endpoint	Mean GFR at week 52 (based on CKD-EPI Eq.)	continuous	Mean and/or geometric mean + 95% CI	Mixed Effects Repeated Measures ANCOVA
	Week-36 LOCF for missing week-52 eGFR	continuous	Mean and/or geometric mean + 95% CI	Mixed Effects Repeated Measure ANCOVA
	Mean GFR at week 52 (based on CKD-EPI Eq.) For Completers	continuous	Mean and/or geometric mean + 95% CI	Mixed Effects Repeated Measure ANCOVA

Table 9. CTOT-15	primary and	secondary	clinical rest	ponse variables
	printing with	. Secondary	cillical ico	ounde vanached

Page 84 of 104

Response type	Response	Measurement	Summary	Models to test for
		Scale	Statistics	treatment effects
		ondary Endpoints	D II	x 1 1
Renal Function and Injury Endpoints	Indicator of week 52 eGFR<60 mL/min/1.7 m ² or day 85 - week 52 eGFR decrease < -10 mL/min/1.7 m ² (composite endpoint based on CKD-EPI Eq.)	dichotomous	Proportion + 95% CI	Log-binomial or Poisson regression
	Mean GFR at week 52 (based on week 52 MDRD4 values)	continuous	Mean and/or geometric mean + 95% CI	Mixed Effects Repeated Measure ANCOVA
	Slope of GFR vs. time Regression over day 85 – week 52, for each treatment arm	continuous	Slope Mean and Std. Error or mean + 95% CI	Mixed effects Repeated Measures ANCOVA
	Incidence of successful tacrolimus withdrawal	dichotomous	Proportion + 95% CI	Log-binomial or Poisson regression
	Incidence of dialysis at day 5	dichotomous	Proportion + 95% CI	Log-binomial or Poisson regression
	Biopsy-confirmed Incidence of an increase of ≥ 1 CAN/IFTA grade, relative to baseline, at each follow-up assessment	Dichotomous (Banff score <1 vs. ≥ 1)	Proportion + 95% CI	Log-binomial or Poisson regression
	Prevalence of CAN/IFTA grades I, II, III at week 52	Dichotomous (1 outcome for each grade)	Proportion + 95% CI	Log-binomial or Poisson regression (1 model per grade)
Incidence and Severity of Rejection and Anti-donor reactivity	Incidence of Acute Rejection (AR) of renal or pancreatic transplant within the first 52 weeks	dichotomous	Proportion + 95% CI	Log-binomial or Poisson regression
	Banff score of the 1 st observed of renal or pancreatic AR within 52 weeks post- transplant	Ordered categories (3 levels)	Proportion + 95% CI	Proportional Odds model
	Highest Banff score observed within 52 weeks post-transplant for either renal or pancreatic transplant	Ordered categories (3 levels)	Proportion + 95% CI	Proportional Odds model

Page 85 of 104

Response type	Response	Measurement Scale	Summary Statistics	Models to test for treatment effects
	Steroid vs. nonsteroidal treatment for renal or pancreatic AR	dichotomous	Proportion + 95% CI	Log-binomial or Poisson regression
	Prevalence of anti- donor HLA antibodies at week 52 for renal or pancreatic transplant subjects	dichotomous	Proportion + 95% CI	Log-binomial or Poisson regression
Cardiovascular + Metabolic	Fasting blood sugar	continuous	Mean and/or geometric mean + 95% CI	Separate ANOVA or ANCOVA at weeks 28 and 52
	HbA1c (baseline through week 52)	continuous	Mean and/or geometric mean + 95% CI	Mixed effects Repeated Measures ANCOVA
	Blood pressure at weeks 28 and 52	Continuous	Mean and/or geometric mean + 95% CI at weeks 28 and 52	ANCOVA at weeks 28 and 52, with use of blood-pressure drugs as a covariate
	Use of BP medications	dichotomous	Proportion + 95% CI	Log-binomial or Poisson regression
	Fasting lipid profiles at weeks 28 and 52	Continuous	Mean and/or geometric mean + 95% CI	Separate ANOVA or ANCOVA at weeks 28 and 52
	Total daily pill count	continuous	Mean + 95% CI tabulated and plotted over time, by trt. group	Separate ANOVA or ANCOVA at day 85 and weeks 28 and 52 (or Poisson Reg)
Safety (for both renal and pancreatic transplant subjects)	Incidence of death or graft loss or undetectable C-peptide separately and as a composite	dichotomous	Proportion + 95% CI	Log-binomial or Poisson regression
	Incidence of any AE	dichotomous	Proportion + 95% CI	Log-binomial or Poisson regression
	Incidence of any SAE	dichotomous	Proportion + 95% CI	Log-binomial or Poisson regression
	Incidence of specific infectious diseases (1 analysis per disease) and/or malignancy	dichotomous	Proportion + 95% CI	Log-binomial or Poisson regression

Page 86 of 104

Response type	Response	Measurement Scale	Summary Statistics	Models to test for treatment effects
	Incidence of specific AEs , by NCI CTC grade and treatment arm	dichotomous	proportion	none
	Specific lab parameters by treatment arm and day/week	continuous	N, min, max, Mean, std. dev	none
	Change from baseline for specific lab parameters by treatment arm and day/week	continuous	N, min, max, Mean, std. dev	none

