In addition, any subjects in the experimental arm of the study will transition from a protocol directed study therapy regimen to a physician directed clinical immunosuppressive regimen. The clinical immunosuppressive regimen may include belatacept and if so, the subject may continue to receive the study supply of belatacept until study completion on August 31, 2016.

B. Informed Consent

The investigator at each site must inform all active subjects that any further low dose CNI withdrawal has been halted and that each subject in the experimental arm will be transitioned from a protocol directed study therapy regimen to a physician directed clinical immunosuppressive regimen. The site investigator or designee must explain during the re-consent process the reason for the premature discontinuation of study therapy and describe in lay terms to the subject and/or the subject's legal representative what is involved in the transition from a protocol mandated therapy regimen to a physician directed clinical immunosuppressive regimen as well as the remaining study follow-up. The subject and/or the subject's legal representative, must read, sign, and date the informed consent form prior to any study-specific procedures.

A copy of the informed consent must be given to the subject and/or the subject's legal representative. The subject and/or the subject's legal representative will be informed that participation in the follow-up portion of the study is voluntary and that he/she may withdraw from the study at any time, for any reason.

C. Description of Amendment Modifications

No further subjects in the experimental arm of the study will undergo low dose CNI withdrawal. In addition, subjects in the experimental arm will transition from the protocol directed study therapy regimen to a physician directed clinical immunosuppressive regimen. If the subject, in conjunction with their treating physician,

opts to remain on belatacept after being reconsented regarding the new findings, they may receive the study supply of belatacept until study completion on August 31, 2016.

Subjects will continue to be followed until study completion based on the existing schedule they are following in Appendices 2, 3 or 4.

D. Drug Accountability

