Maintenance Immunosuppression	Mycophenolate Acid	BOTH STUDY GROUPS : CellCept [®] (Mycophenolate Mofetil- MMF) will be administered at a target dose of 1000 mg PO or IV BID beginning on the day of surgery or post- operative day 1 depending upon when during the day the surgery is completed (maximum MMF dosing is 2G per day). MMF will be adjusted based on clinical complications (such as neutropenia). Myfortic [®] (mycophenolate sodium) may be used as a replacement for MMF. Mycophenolate sodium will be dosed at 720 mg PO or IV BID. Mycophenolate sodium will be adjusted based on clinical complications.
Maintenance Immunosuppression	Prograf® (tacrolimus)	Tacrolimus may be discontinued or target levels adjusted at the discretion of the Investigator. CONTROL ARM: The site investigator will identify a starting tacrolimus dose at their discretion in order to achieve the target trough levels no later than 5 days post-transplantation. Tacrolimus dosing will be initiated on the day of surgery or post-operative day 1 depending upon when during the day the surgery is completed, then adjusted to target trough levels of 8-12 ng/ml during the first 24 weeks post-transplant, then adjusted to target trough levels of 5-8 ng/ml thereafter. INVESTIGATIONAL ARM: The site investigator will identify a starting tacrolimus dose at their discretion, in order to achieve the target trough levels no later than 5 days post-transplantation. Tacrolimus dosing will be initiated on the day of surgery or post-operative day 1 depending upon when during the day the surgery is completed. The dosage will be adjusted to achieve the following therapeutic trough levels: 5-8 ng/ml during the first 24 weeks post-transplant and then 3-5 ng/ml until day 280 (week 40). Subjects may be withdrawn if they meet all the criteria defined below. Tacrolimus Withdrawal: Subjects participating in the Investigational Arm will be considered eligible for withdraw of tacrolimus once they have reached the week 40 study visit, if all of the following is met:
		 No evidence of cellular or antibody mediated rejection in the first 280 days post- transplant. Stable renal allograft function as measured by serum creatinine over the preceding 90 days.

Protocol CTOT-15					 
	3. Stable pancreatic fund serum amylase/lipase			ng blood sugars, HbA1c, a	and
	4. The absence of donor		-	ransplant.	
	If eligible for withdrawal, t period. The chart below sh tacrolimus dose.	•			nd

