13.3 Sample Size and Power Calculations

We have used data from the belatacept phase II and DIRECT studies and from the literature (Grewal and Blake 2005) to provide expected values for the GFR standard deviations shown in Table 10 below. Sample size calculations for these analyses were performed using NCSS-PASS software.

In the primary endpoint analysis, we will compare the mean GFR between the study groups at 12 months. With the sample sizes fixed, a priori, at 30 subjects in each of the two treatment arms, the following table shows the smallest treatment mean GFR differences (i.e. effect sizes) we will be able to declare significantly different, with 80% power and Type I error rates of 0.05 and 0.10:

Table 11 - Smallest Detectable Difference in GFR at 12 Months for Different Standard Deviationsand Alpha Levels

GFR Standard Deviation	Alpha Level	Smallest Detectable Difference in GFR (mL/min/1.7 m ²)
16	0.05	12.0
	0.10	10.5
20	0.05	15.0
	0.10	13.0
24	0.05	18.0
	0.10	16.0

This study has been powered to be able to detect minimum detectable differences in the primary endpoint at both the 0.05 and 0.10 levels that are clinically relevant as shown in Table 9 above. When reporting results of the primary endpoint analysis, we will report a p-value as significant at the 0.10 level if it is less than 0.10 and as significant at the 0.05 level if it is less than 0.05. As previously stated, all secondary endpoint analyses will be performed at the 0.05 level.

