Monitoring Assay Development: BLOOD	Vacutainer Tube			Л		Л				Л		~				л	Λ
Viral Monitoring by PCR (CMV, BKV, JCV, HHV6, HHV7) AND Viral Monitoring Assay Development (HHV3 (varicella zoster), HHV6 (roseola), HHV7 (cofactor CMV), polyoma JC, WC,KI): PLASMA	5mL PPT Tube OR plasma collected from the CPT tubes for Intracellular Cytokine Staining Viral Phenotyping			X		Х				X		Х				Х	Х

1. If a subject develops anti-donor alloantibodies or de novo anti-HLA (PRA >25%), the test must be repeated on a fresh sample and confirmed within 4 weeks.

2. For Cause Biopsy specimens should be collected at times of graft dysfunction, and prior to initiating therapy.

3. If blood samples are collected for a For-Cause biopsy AND are within 2 weeks of a scheduled visit, then the samples will also be used for the scheduled visit.

4. The first dose of NULOJIX® (belatacept) will be administered approximately 24-48 hours after the last dose of Thymoglobulin® (Anti-Thymocyte Globulin- Rabbit).

5. The results of the non-HLA Ab/Anti-HLA Antibodies/DSA drawn at week 36 will be sent back to the clinical sites in order to make a decision regarding tacrolimus withdrawal at week 40.

6. At week 40, subjects eligible for withdrawal will be weaned over a 4-8 week period based on the protocol.

7. Tacrolimus dosing will be collected following week 44 on subjects who were not eligible for withdrawal or failed withdrawal.

8. During tacrolimus weaning and for 6 weeks post tacrolimus withdrawal, subjects will have weekly labs that include serum creatinine, fasting glucose, amylase and lipase.

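### The primary model makes eGFR linear in time, so its week-52 contrast can miss the week-52 mean difference that defines the endpoint

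*Combined protocol and SAP*

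**What the plan says.** Sections 1.4 and 13.1 fix the endpoint at one time point: "Analysis of the primary endpoint will be based on outcomes measured at 52 weeks post-randomization". Section 13.3 powers the same quantity: "In the primary endpoint analysis, we will compare the mean GFR between the study groups at 12 months".

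Section 13.2.1 puts the analysis in an MMRM framework, "wherein repeated measures of eGFR at weeks 4, 12, 28, 36 and 52 will be modeled as a linear function of time" in the two treatment groups, and contrasts the arms at week 52. Table 9 adds only that the model is a mixed-effects repeated-measures ANCOVA. Nowhere is visit named as a factor, or a treatment-by-visit term specified.

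Model assumptions are to be checked with residual plots. The stated remedy is: "If the assumptions fail, a suitable transformation (e.g., natural logarithms) will be found and the data will be reanalyzed on the transformed scale". Of the two sensitivity analyses, one carries week 36 forward and is then to "perform the ANCOVA as currently specified"; the other keeps completers only.

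On the regimens, section 8 gives the arms different tacrolimus trough targets from the start and lowers both after week 24. Only the investigational arm can then be weaned (Appendix 2, footnote 6): "At week 40, subjects eligible for withdrawal will be weaned over a 4-8 week period based on the protocol". The amendment text at the front of the protocol later limits this: "No further subjects in the experimental arm of the study will undergo low dose CNI withdrawal".

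**The concern.** A straight line per arm over weeks 4 to 52 predicts the week-52 mean from all five visits. If the arm difference is constant or changes linearly, the prediction is unbiased and slightly more precise than the week-52 means. If the difference bends, the contrast no longer estimates the stated endpoint. Curvature shared by both arms cancels with complete data, so what matters is the shape of the difference.

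The protocol gives reasons to expect a bend. Treatment changes in steps, one of them applies to a single arm from week 40, and week 52 is the only modelled visit after that step. A benefit or loss of function that appears late would be diluted. A benefit reached by mid-follow-up and then held would be inflated. An early difference gone by week 52 could be reported as a week-52 difference.

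**Working it through.** **Inputs from the documents.** Visits at weeks 4, 12, 28, 36, 52, linear time, contrast at week 52 (13.2.1). 30 per arm, SD 16, detectable difference 12.0, 80% power, two-sided 0.05 (13.3, Table 11).

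**Assumptions, since the documents give none.** Within-subject covariance: compound symmetry (CS) with correlation 0.5–0.8, or AR(1) with 0.9 per 8 weeks. Shape of the arm difference: several, listed below. Arm-specific slopes and complete data unless stated.

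**Step 1: Table 11.** For a comparison of week-52 means, SE = 16·√(2/30) = 4.13. A difference of 12 gives noncentrality 12/4.13 = 2.90 and, by the noncentral t with 58 df, power 81%. The smallest detectable differences at 0.05 are 11.77, 14.71 and 17.65 for SD 16, 20 and 24. At 0.10 they are 10.39, 12.99 and 15.59. Table 11 rounds these up, so it describes a plain comparison of week-52 means.

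**Step 2: weights in the linear-time contrast.** w = [1, 52](X′V⁻¹X)⁻¹X′V⁻¹, with X = [1, t]. Under CS (any correlation), or a random intercept and slope, this reduces to 1/5 + 25.6·(t − 26.4)/1459.2, where 26.4 is the mean visit week and 1459.2 the sum of squared deviations. Week 52: 0.2 + 655.36/1459.2 = 0.649.

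| Covariance | wk 4 | wk 12 | wk 28 | wk 36 | wk 52 |
|---|---|---|---|---|---|
| CS | −0.193 | −0.053 | 0.228 | 0.368 | 0.649 |
| AR(1) 0.9 per 8 weeks | −0.093 | 0.050 | 0.058 | 0.068 | 0.917 |

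**Step 3: estimate and power when the true week-52 difference is 12.** Estimate = weights × shape. The SE of the linear contrast is 4.13 divided by 1.101 (CS 0.5), 1.037 (CS 0.8) or 1.003 (AR(1)), that is 3.75, 3.98 or 4.12.

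| Shape of arm difference | Share recovered, CS / AR(1) | Estimate, CS / AR(1) | Power, CS 0.8–0.5 | Power, AR(1) |
|---|---|---|---|---|
| Constant, or linear from 0 | 100% / 100% | 12.0 / 12.0 | 84–88% | 82% |
| Two-thirds to wk 36, full at wk 52 | 88% / 97% | 10.6 / 11.7 | 74–79% | 80% |
| Half to wk 36, full at wk 52 | 82% / 96% | 9.9 / 11.5 | 69–74% | 78% |
| Only at wk 52 (extreme) | 65% / 92% | 7.8 / 11.0 | 49–53% | 75% |
| None to wk 12, full from wk 28 | 125% / 104% | 14.9 / 12.5 | 96–97% | 85% |

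Week-52 means give an expected 12.0 and 81% power in every row.

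**Step 4: false rejection.** If the arms differ by 8 to week 36 and by 0 at week 52, the model reports 8·(1 − 0.649) = 2.8 under CS and rejects in about 11% of trials at nominal 5%. Under AR(1) it reports 8·(1 − 0.917) = 0.7 and rejects in 5.3%.

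**Step 5: missing data.** With 10%, 20% or 30% of week-52 values missing at random, the week-52 weight falls to 0.62, 0.59 or 0.55 (CS) and 0.86, 0.81 or 0.74 (AR(1)), so the assumed line matters more.

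**Step 6: categorical visit.** With treatment-by-visit terms and complete data the weights are (0, 0, 0, 0, 1). The contrast is the week-52 mean difference for any shape, and Table 11 stands.

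**The case against.** - **MMRM usually means visit as a factor.** The slope is also a separate secondary endpoint, so the wording may be loose. That is possible, but the literal text says linear and nothing corrects it. If categorical visit was intended, the fix merely states it.
- **There is a check.** Residual plots can reveal a wrong time form. This stands in part: what is missing is a remedy. Plots with 30 per arm are a weak check, and transforming the outcome does not in general cure a late bend in the arm difference. Neither sensitivity analysis is described as changing the time form.
- **The size rests on assumptions.** This stands. Under AR(1) per 8 weeks every shape in the table recovers 92–104%. With AR(1) 0.9 indexed by visit number, the week-52 weight is 1.025 and a late-only difference of 12 is read as 12.3, so even the direction depends on the covariance. Section 13.2.1 does not fix one.
- **A withdrawal-only effect is unlikely.** This stands. Troughs differ from the start, belatacept begins on day 5, withdrawal required four criteria, and further withdrawal was halted. The late-only row is a bound; the milder rows are more plausible. For the two-thirds shape at CS 0.5, the linear model even has slightly lower root mean square error (4.01 against 4.13), though at CS 0.8 it is higher (4.22).
- **Non-linear differences can cancel.** Under CS, differences of −21.8 at week 4, 0 at weeks 12 to 36 and 12 at week 52 return 12.0. Such cases are contrived and depend on the covariance.
- **Falling weights under missing data do not alone prove harm.** This is fair: a categorical model also borrows from earlier visits. It does so without imposing a line on the means.

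**Conclusion.** The concern holds. As written, the primary contrast and the stated endpoint are different quantities unless the arm difference is linear in time, and the plan neither justifies that assumption nor says what to do if it fails. The consequence ranges from negligible (AR(1), gradual separation) to substantial (CS, late or plateauing separation), and the documents give no basis for choosing between them. The claim in section 13.2.1 that the comparison is robust to dropout under missing at random also needs a correct model for the means. The point should be fixed; it does not invalidate the design or Table 11.

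**What to change.** In section 13.2.1, replace the linear-time wording with:

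> eGFR will be modeled with treatment, visit (categorical: weeks 4, 12, 28, 36, 52) and treatment-by-visit interaction, with unstructured covariance and Kenward-Roger degrees of freedom. If this does not converge, heterogeneous compound symmetry and then a spatial-power structure will be used, in that order. The primary estimate is the week-52 treatment contrast.

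Use the same visit coding in both sensitivity analyses. Keep linear time only for the secondary slope endpoint in Table 9. The pattern-mixture option for failure of missing at random can stay.

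Cost: no new data. The mean model has 10 parameters instead of 4, and an unstructured covariance has 15; the power figures above treat the covariance as known. If the trajectories are truly linear, the SE is about 4–10% larger under CS 0.8–0.5 (power 81% instead of 84–88% for 12 mL/min at SD 16) and under 1% larger under AR(1). Because 13.2.1 is protocol text, the change is an amendment that needs approval under section 16.1. Section 10.4.1 keeps analyses blinded to treatment until database lock, apart from DSMB safety reviews, so the wording can be settled before lock without knowledge of results by arm.
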